8. STUDY PROCEDURES

8.1 Screening and Eligibility Assessment

The outline of the patient flow through the study is highlighted Appendix 1 (pg. 51). Patient recruitment, which will not commence until Sponsor 'green light' has been given, will be co-ordinated via the research team at the Leicester Diabetes Research Centre with support from divisions 2 and 5 of the Clinical Research Network for the East Midlands. As the Leicester Diabetes Centre is located within a secondary care facility with specialist diabetes clinics we have access to more than 8000 patients through the University Hospitals of Leicester NHS Trust. Many more patients with Type 2 Diabetes are being treated within primary care across GP practices in Leicester City and Leicestershire County.

The study will recruit men and postmenopausal women with Type 2 Diabetes who are on stable dose of metformin or managed by lifestyle modification only. Pre-menopausal women are not being recruited to this study as the menstrual cycle can affect appetite hormone concentrations.

8.2 Recruitment Strategy

The recruitment phase will commence as soon as ethical, research governance and regulatory approval has been granted and the Sponsor green light has been given. Please see Appendix 1 (pg. 52) for participant identification pathway. Potential participants will be identified and/or contacted using direct and opportunistic marketing, using both verbal and written information about the research study, including invitation packs and a call to participants approximately 2 weeks after each mailing. If GP practices are willing to add notes and/or reminders to patient records within SystemOne to facilitate recruitment, then the study team will work with the CRN and GP practices to add notes and/or set-up reminders on eligible patient records for the GP or Diabetes Specialist Nurse to inform about the trial during routine appointments.

The following recruitment activities will be used:

- 1. Primary care
 - a. GP practices
 - b. Retinal screening clinics

2. Secondary care

- a. Attendance at UHL Outpatients Clinics, for example:
 - i. Diabetes
 - ii. Cardiology and Hypertension
 - iii. Obstructive Sleep apnoea
 - iv. Ophthalmology
 - v. Lipid

b. Community Clinics

- i. Hinckley
- ii. Market Harborough

c. Secondary Care Databases

3. Previous research participants

- a. At the Leicester Diabetes Centre, around 4200 adults have recently been screened for two diabetes prevention studies, namely "Let's Prevent Diabetes" and "Walking Away from Diabetes". Of these, around 5% (~210) of participants had Type 2 Diabetes at baseline and were withdrawn but who had given consent to be contacted to take part in future studies. We will recruit from this accessible pool of newly diagnosed Type 2 Diabetes patients.
- b. Leicester Diabetes Centre also has a volunteer database of people with Type 2 Diabetes who have given consent to be contacted and we will contact these individuals.
- c. CODEC study participants who have given consent to be contacted for future research.

4. Key people in community/community events and meetings

a. Identify and engage key people in the community including pharmacists, GP mentors, other Healthcare professionals and community workers to distribute both verbal and written information about the research study.

5. Recruitment/health fairs in community

a. Participate in community events and open days to publicise the study and distribute information. This will consist of having a stand with all the study information and/or presenting the study at these events.

6. Study advertisement

- a. Publicise the study through the local and social media including local radio stations and press releases, Twitter and Facebook.
- b. Distribute posters to publicise the study in primary and secondary care waiting rooms and within the community e.g. supermarkets, libraries, gyms and community centres.
- c. Advertise the study on the University Hospitals of Leicester NHS Trust and University of Leicester intranet which will include the study acronym and logo, a description about the study and contact details of the research team.

8.3 Participant Flow

Visit 0 (Screening Visit, -1 week to -2 days), Visit 1 (Baseline Visit- 0 weeks), Visit 2 (2 weeks \pm 5 days), Visit 3 (6 weeks \pm 5 days), Visit 4 (12 weeks \pm 5 days), Visit 5 (Final Visit - 24 weeks \pm 5 days), Follow-up telephone call (1 week \pm 3 days after medication completion).

8.4 Informed Consent (Screening Visit, Visit 0, only)

Informed written consent will be obtained from all participants prior to any study procedures and only after they have had sufficient time (at least 48 hours) to read through the patient information sheet and ask any questions related to the study. The study clinician who has undergone consent training and holds an up-to-

date Good Clinical Practice (GCP) certificate will obtain consent and this will be in the form of the participant's and consent taker's dated signatures. The participant will be given a copy of the signed informed consent form along with a copy of the patient information sheet, and a copy retained in the medical records and the original retained in the Investigator Site File. Consent for ongoing participation will be checked at each study visit and documented in the clinical notes and CRF by the study clinician.

8.5 Investigations

Primary Outcome Measurement

Appetite Hormones (visits 1, 2, 3, 4, 5) - Ghrelin, PYY, GLP-1

The primary outcome is change in appetite hormones from baseline to week 24 and between groups.

For this, participants are required to fast for 10 hours before study visits 1-5, and prior to the measurement of appetite hormones at each visit, there will be dietary standardisation. Specifically, there will be a 48 hour standardisation plan incorporating a 24 hour meal standardisation plan, and on the day of their study visit a standardised breakfast. The standardisation plans are described below:

> 48 Hour pre-visit Standardisation

For the 48 hours before study visits 1-5, participants will be asked to refrain from:

- completing any structured form of physical activity,
- consuming alcohol
- consuming caffeine

Participants will be issued with food and drink diaries (see Section 8.7, pg. 26) at the familiarisation visit (visit 0) within which to record their intake and this will be reviewed at each visit to ensure that they are adhering to the 48 hour restriction period. Participants will be asked whether or not they have completed any structured form of physical activity at each visit.

24 Hour Meal Standardisation

In addition to the 48 hour pre-visit standardisation described above, for the 24 hours before study visit 1-5, participants will be asked to:

- standardise their food and drink intake (i.e., to consume the same food and drinks before each study visit)
- consume the standardised evening meal provided to them at least 10 hours before their visit. This
 will be based on their energy requirements**. A set meal will be provided dependent on whether
 their energy requirement is above or below a 1500 Kcal threshold.
- continue to fast until their visit (they will be provided with a standardised breakfast at their visit)

Participants will be issued with food and drink diaries (see Section 8.7, pg. 26) at the familiarisation visit (visit 0) within which to record their intake and this will be reviewed at each visit to ensure that they are adhering to the 24 hour meal standardisation period.

**participants daily energy requirement will be estimated at their familiarisation visit (visit 0) using the Mifflin St Jeor Equation (MSJE).

Breakfast Standardisation

On the morning of study visits 1-5, participants will be provided with a standardised breakfast meal representing 33.3% of their daily energy requirement* with a macronuritent content of:

- 50% carbohydrate
- 15% protein
- 35% fat

*Note that participants' daily energy requirement will be estimated at the baseline visit (visit 1) using indirect calorimetry and multiplying by the appropriate physical activity level (PAL). If for any reason indirect calorimetry cannot be used, energy expenditure will be estimated using the Mifflin St Jeor Equation (MSJE) instead.

The appetite hormones acylated ghrelin (hunger stimulating) and GLP-1 (appetite-inhibiting) will be measured using commercially available ELISA kits. Total PYY (appetite-inhibiting) will be measured using ELISA. All hormones will be measured in fasting conditions and after the standardised breakfast meal at 7 time points during each visit. Specifically, using cannulation of the participant's forearm, blood samples will be collected at baseline (i.e., pre-standardised breakfast) and then at regular 30 minute intervals starting from the 'time of the last mouthful of breakfast' at 30 minutes, 60 minutes, 90 minutes, 120 minutes, 150 minutes, and 180 minutes. A total of 7 samples will be taken during each visit. A total of 130ml (approximately 18ml per sample) will be collected at each visit. Blood will be collected into pre-cooled blood collection syringes containing necessary preservatives to ensure sample viability for hormone/metabolite biochemical analysis. Blood collection syringes will be prepared and kept on ice prior to their use. After each blood withdrawal the cannula will be flushed with saline to maintain patency. Once blood samples have been collected they will immediately be spun in a refrigerated centrifuge (4°C) and the plasma will be obtained and aliquoted into eppendorf tubes. These samples will then be frozen (initially at -20°C but then transferred to -80°C on the same day as collection) until required for analysis. The appetite hormone samples will be transported to Loughborough University for subsequent analysis using dry ice.

At 30 minute intervals and in conjunction with blood sampling, the participants will complete a set of appetite rating scales to assess subjective perceptions of hunger, fullness, satisfaction and prospective food consumption.

Secondary Outcome Measurements

Body Composition (visits 1, 5) – DEXA scan

Body composition (fat mass and fat free mass) will be assessed by DEXA scanning at baseline and study end visits using a scanner situated at the Leicester Diabetes Centre according to standard operating procedures.

Biochemical Analysis (visits 1, 2, 3, 4, 5)

Blood tests for FBC, U+E, LFT, lipid profile, HbA1c, FPG, eGFR, glucagon, insulin, leptin, C-peptide, FFA and CRP will be taken (see Abbreviations pg. 11). Urinary glucose excretion (UGE) will be quantified by timed collection to match with appetite hormone sampling. FBC, U+E, lipids, HbA1c, FPG, eGFR and CRP will be

measured once during each visit. Insulin, glucagon, glucose, leptin and C-peptide will be measured at 7 time points specifically at baseline (pre-standardised breakfast), 30 minutes post-breakfast and then 60 minutes, 90 minutes, 120 minutes, 150 minutes and 180 minutes post-breakfast to correspond with the appetite hormones. These blood samples will be analysed at Leicester General Hospital either by the main hospital diagnostic laboratory or by the Research Scientist based at Leicester Diabetes Centre and then disposed of in accordance with the Human Tissue Authority's Code of Practice.

Following analysis, where a participant has consented, samples will be stored indefinitely for future research use.

Energy Expenditure (visits 1, 2, 3, 4, 5)

Indirect calorimetry will be used to assess resting energy expenditure (REE) at baseline, 2, 6, 12 and 24 weeks. This will be measured using a ventilated hood system at the Leicester Diabetes Centre where the participant will place their head under the hood to enable measurement of all expired gases over a predetermined time period according to standard operating procedures.

Physical Activity (visits 0, 3, 4, 5)

An ActiGraph accelerometer will be provided to the participant to be worn for 8 days (including the clinic day and 7 full consecutive days thereafter) for assessment of step count as a measure of physical activity at visit 0, 6, 12 and 24 weeks. An activPAL inclinometer will also be used to assess posture (i.e., sitting/lying, standing and stepping) for 9 days (including the clinic day and 8 consecutive days thereafter) at visit 0, 12 and 24 weeks. Should study visits occur directly before or during certain holiday periods i.e. Easter, Christmas and New Year, monitors will be sent to participants via the postal system after the holiday period. The study team wish to avoid these holidays periods as it is not habitual behaviour. These will be applied according to Leicester Diabetes Centre standard operating procedures. A log of sleep, wake and monitor removal times will be completed by the participants.

Study Questionnaires (visits 1, 2, 3, 4, 5)

The participant will be asked to complete the following validated questionnaires (see Appendix):-

- > Three-Factor Eating Questionnaire this will assess the participant's current eating habits
- ➤ International Physical Activity Questionnaire (IPAQ) this will assess habitual physical activity in several domains including occupation, leisure, housework
- Visual Analogue Scale (VAS) which will measure perceived hunger, fullness, satisfaction and prospective food consumption ratings

Other Measurements and Data Collection

Anthropometric Measures (visits 0, 1, 2, 3, 4, 5)

Body weight will be measured to the nearest 0.1kg, body fat percentage will be measured to the nearest 1% and muscle mass will be recorded to the nearest 0.1kg using bioelectrical impedance equipment (i.e., Tanita™ scales) while the participant is wearing no shoes and socks and after the removal of any heavy items of clothing.

Height will be measured using a portable stadiometer to the nearest 0.5cm with the participant wearing no shoes.

Waist circumference will be measured to the nearest 0.5cm as the midpoint between the lower costal margin and iliac crest. Hip circumference will be measured to the nearest 0.5cm at the maximum extension of the buttocks ensuring the tape measure is at the same level around the body. Both measures should be taken over underwear or light clothing with the subject standing with their feet together and breathing lightly.

Arterial blood pressure will be measured using an automated sphygmomanometer for the arm whilst the patient is seated after resting quietly for five minutes. Three measurements will be obtained for blood pressure and an average of the last two will be used. Standing blood pressure will also be collected. The measurement will be taken after the patient has been standing for three minutes with their feet hip-width apart and their arm supported at their side i.e. not hanging freely.

Demographics (Visit 0)

The date of birth, gender, race, smoking and drinking habits will be recorded by the doctor at the familiarisation visit (visit 0).

Medical History (Visit 0)

Details of any history of disease or surgical interventions will be recorded by the doctor at the familiarisation visit (visit 0).

Physical Examination (Visit 0)

A general physical examination will be performed by the doctor at the familiarisation visit (visit 0).

Randomisation to Study Medication (Visit 1)

At visit 1, participants will be randomised to either (i) Empagliflozin (Jardiance™) 25mg once daily, (ii) placebo once daily, (iii) Empagliflozin (Jardiance™) 25mg once daily and energy restriction diet, or (iv) placebo once daily and energy restriction diet using a web-based randomisation system supplied by the 3rd party company (Sealed Envelope Ltd.).

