6. STUDY DESIGN

6.1 Trial Summary

This trial is a randomised, double-blind placebo-controlled trial conducted over 24 weeks in male and postmenopausal female participants with Type 2 Diabetes on lifestyle control or stable metformin dose only to compare the effects of Empagliflozin (Jardiance™) on appetite and weight regulation compared with placebo and energy restriction diet.

Participants will be randomised to one of four arms at baseline:-

- (i) Empagliflozin (Jardiance™) 25mg once daily
- (ii) Placebo once daily
- (iii) Empagliflozin (Jardiance™) 25mg once daily and energy restriction diet
- (iv) Placebo once daily and energy restriction diet

Participants will be stratified for age [1. \leq 50years 2.>50years] and body mass index (BMI; [1. BMI 25.0-29.9kg/m² 2. BMI \geq 30.0kg/m²]).

The study design is illustrated in Figure 1 (pg. 17).

Participants will attend a screening (familiarisation) visit prior to the start of the study followed by 5 visits over 24 weeks.

The first visit (visit 0) is the Screening (Familiarisation) Visit and will occur not more than 1 week nor less than 2 days before the Visit 1 (Baseline visit). Visit 0 (approximately 2 hours) will involve a review of inclusion/exclusion criteria, an explanation of study procedures and obtaining verbal and written consent from participants by a medically qualified doctor. In addition, blood will be taken for HbA1c and renal function and participants will be issued with 2 physical activity monitors along with a log of wear, sleep and waking, and a food and drink diary for completion throughout the course of the study.

Visit 1 is the Baseline visit lasting between 6-8 hours divided into morning and afternoon sessions of procedures including blood and urine tests, completion of questionnaires, dual energy X-ray absorptiometry (DEXA) imaging and energy expenditure (indirect calorimetry). Randomisation to one of the four arms will also occur during this visit. Procedures will be conducted and supervised by the research team comprising of study clinician, trained research nurse and healthcare assistant (HCA).

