Visits 2 (occurs 2 weeks (±5 days) after visit 1, lasting between 6-8 hours), 3 (6 weeks (±5 days), lasting between 6-8 hours), 4 (12 weeks (±5 days), lasting between 6-8 hours) and 5 (24 weeks (±5 days), lasting between 6-8 hours) will be divided into morning and afternoon sessions of procedures which will be supervised by the research team. There will be final review by a medically qualified doctor before the participant completes the study on this visit.

Figure 1 - Study Design

Participants enrolled from primary and secondary care / previous studies from which participants have agreed to be contacted for future studies / diabetes databases and registries

Participants with stable type 2 diabetes who fulfil inclusion criteria will be sent information pack and invitation to enrol

Inclusion Criteria

- Males/postmenopausal females aged 30-75y
- Type 2 Diabetes on lifestyle control or stable dose of metformin for at least 3 months
- Stable weight (<5% change in body weight in last 3 months)
- HbA1c 42-86mmol/mol (6.0-10%)
- eGFR≥60ml/min/1.73m²
- BMI≥25kg/m²
- Able to give informed consent
- Able to understand English

Visit 0 (Familiarisation Visit)

- Inclusion/Exclusion criteria
- Explanation of Study Procedures
- Informed consent
- Medical History, Physical Examination, Screening blood tests

Baseline Clinic Visit – Visit 1 (Dispensing Visit)

- Anthropometric measures
- Lifestyle (IPAQ) and Appetite (VAS, 3 factor eating, food preference) measures (questionnaires)
- Biochemical measures (including insulin, glucose, glucagon, leptin, HbA1c, UGE, appetite hormones [fasting and post-meal]) (ghrelin, PYY, GLP-1)
- Resting energy expenditure (indirect calorimetry)
- Physical activity (accelerometer, inclinometer)
- Body composition fat and fat free mass (DEXA)
- Randomisation (1:1:1:1) stratified by age and BMI

Placebo

Empagliflozin
25mg daily

Placebo and EnergyRestriction Diet

Visit 2 (2 weeks ± 5 days)
(Dispensing visit)

Visit 3 (6 weeks ± 5 days)

Visit 4 (12 weeks ± 5 days)
(Dispensing visit)

Final Visit – Visit 5 (24 weeks ± 5 days)

Follow-up Telephone Call (1 week ± 3 days after

medication completion)

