8.8 Subsequent Assessments

Table 1 (pg. 27) shows the visit numbers and window periods for the visits. A detailed description of each assessment is provided in Section 8 – Study Procedures (pg. 21).

Visit 0 (Screening Visit) – clinic visit (- 1 week to - 2 days)

During this visit, there will be an eligibility check of inclusion/exclusion criteria, concomitant medications recorded and a safety assessment including physical examination performed. Screening blood tests will be performed if not checked in the last 3 months. Participants will be provided with a diary within which to record their consumption of food and drink throughout the course of the study. Specifically, participants will be asked to record all food and drink consumed, including details about the amount/portion size consumed, a description of what was consumed (i.e., the brand) and the time that it was consumed for a minimum of four days to include the 48 hour restriction period. The diaries will be used to determine whether or not participants have adhered to the 48 hour pre-visit restriction period (see Section 8.4. pg. 22) and their daily energy restriction diet prescription (if applicable; see Section 8.5, pg. 25). The diaries will be checked by a member of the research team at each visit.

Visit 1 (Baseline Visit, 0 weeks) – clinic visit Dispensing Visit

During this visit, there will be a check for ongoing consent to participate in the trial, record of concomitant medications and baseline blood tests performed including renal and liver function tests for safety. Study drugs will be dispensed following randomization. Energy restriction diet will be prescribed if participants are randomized to this intervention.

Visit 2 – clinic visit at 2 weeks (- 5 days to + 5 days)

Dispensing Visit

During this visit, there will be a check for ongoing consent to participate in the trial, record of concomitant medications and blood tests performed for safety including renal and liver function tests. There will be assessment of study drug compliance and/or energy restriction diet compliance. Drug accountability will be performed.

Visit 3 – clinic visit at 6 weeks (- 5 days to + 5 days)

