5.2 Secondary outcome definitions

Below is a list of all of the secondary outcomes collected at baseline and at least one followup visit. Outcomes measured at 2, 6 and 12 weeks will be treated as secondary outcomes.

(i) Appetite hormones ghrelin and GLP-1 and appetite perception Ghrelin and GLP-1 will each be recorded in the same manner as the primary outcome, i.e. as time averaged AUC.

(ii) Resting energy expenditure

(iii) Change in blood and urine biochemical parameters.

- Insulin time averaged AUC
- Glucose time averaged AUC
- Glucagon time averaged AUC
- C-peptide time averaged AUC

The above biochemical parameters will be measured at 7 time points specifically, fasted (pre-standardised breakfast), 30 minutes post-breakfast and then 60 minutes, 90

minutes, 120 minutes, 150 minutes and 180 minutes post-breakfast. Time averaged AUC values will be calculated as per that for PYY.

- Leptin
- HbA1c
- C-reactive protein
- Fasting plasma glucose
- Lipids (total HDL and LDL cholesterol, FFAs)
- eGFR
- urinary glucose excretion
- ALT
- Leptin

(iv) Physical activity measures:

 ActiGraph for assessment of daily step count and daily time spent sedentary and in light-intensity and moderate-to-vigorous intensity physical activity (including only those people with at least 3 days of data)

(v) Study questionnaires

- Three-Factor Eating Questionnaire this will assess the patient's eating traits (restraint, disinhibition, hunger)
- International Physical Activity Questionnaire (IPAQ) —to assess walking, moderate and vigorous activities, along with time spent sedentary.
- Visual Analogue Scale (VAS) which will measure perceived hunger, fullness, satisfaction and prospective food consumption ratings. VAS is measured at every time point as per the blood samples and so will also be analysed as an AUC measure, as per that for PYY.

(vi) Anthropometric measures:

- Body weight (kg)
- Body fat (%)
- Fat mass (kg)
- Bone mass (kg) and density (g/m²)
- Muscle mass (kg)
- Waist circumference (cm)
- Hip circumference (cm)

(vii) Cardiovascular measures:

- Blood pressure (mmHg)
- Resting heart rate (bpm)

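### Baseline activity monitoring cannot finish before randomisation, the 24-week monitoring week follows the final visit, and the SAP has no date rule for either

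*Protocol*

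**What the plan says.** **Wear period.** Protocol 8.5 asks for the ActiGraph "to be worn for 8 days (including the clinic day and 7 full consecutive days thereafter", at visit 0 and at 6, 12 and 24 weeks. The activPAL is worn "for 9 days (including the clinic day and 8 consecutive days thereafter) at visit 0, 12 and 24 weeks". If a visit falls just before or during certain holidays, monitors are posted after the holiday.

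**Baseline.** Protocol 6.1 and Table 1 have the baseline monitors issued at visit 0, which "will occur not more than 1 week nor less than 2 days before the Visit 1 (Baseline visit". Of visit 1, 6.1 says: "Randomisation to one of the four arms will also occur during this visit". Protocol 8.8 adds: "Study drugs will be dispensed following randomization"; the diet is prescribed at the same visit. Protocol 8.5 also sets a restriction: "For the 48 hours before study visits 1-5, participants will be asked to refrain from" structured physical activity, among other things.

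**Week 24.** Visit 5 is the final visit. A doctor's review takes place "before the participant completes the study on this visit" (Protocol 6.1). Drug accountability is performed and no dispensing is listed (8.8, Table 1). Unused medication is returned at each visit (9.3).

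**Use of the data.** Protocol 6.3 names change in physical activity from baseline to study end as a secondary endpoint; Protocol 5.3 calls the secondary endpoints exploratory. SAP 5.2 lists ActiGraph outcomes, "including only those people with at least 3 days of data". SAP 5.3.3 applies the primary model, with adjustment for the baseline value and stratification factors, plus ActiGraph wear time. Neither document says on which side of visit 1 or visit 5 a counted day must fall.

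**The concern.** A baseline covariate should be measured before treatment can affect it, and a study-end value should describe participants while they are treated. Here every wear window starts on the clinic day and runs forward. At baseline that carries wear into the period after randomisation; at week 24 it carries wear past the end of the study visits. The diet is not blinded (SAP 2.8), so a change in behaviour within days of visit 1 is plausible in the diet arms.

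If the baseline already contains some of the treatment effect, adjusting for it removes part of that effect from the follow-up comparison. If the 24-week week is mostly off drug, a drug effect on activity may have faded before it is measured. Both push towards no difference. Activity is part of the energy-balance account of why observed weight loss falls short of prediction, so a null result could be misread as ruling activity out.

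**Working it through.** **The documents' own figures.** ActiGraph: 1 + 7 = 8 days. activPAL: 1 + 8 = 9 days. Five half-lives: 5 × 12.4 h = 62 h, which Protocol 8.10 rounds up to 72 h. All reproduce.

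**Baseline day count.** Let visit 1 be day 0 and visit 0 be day −g, with g = 2 to 7. Full wear days run from −g + 1 to −g + 7 (ActiGraph) or −g + 8 (activPAL). Days −2 and −1 are taken as the 48 h restricted period. The part-day at visit 0 is not counted.

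| Gap g (days) | Full days before visit 1 | Of these, outside the 48 h period | Day of visit 1 | Full ActiGraph days after it | activPAL days after it |
|---|---|---|---|---|---|
| 2 | 1 | 0 | 1 | 5 | 6 |
| 3 | 2 | 0 | 1 | 4 | 5 |
| 4 | 3 | 1 | 1 | 3 | 4 |
| 5 | 4 | 2 | 1 | 2 | 3 |
| 6 | 5 | 3 | 1 | 1 | 2 |
| 7 | 6 | 4 | 1 | 0 | 1 |

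For the last wear day to precede visit 1, −g + 7 ≤ −1 gives g ≥ 8 (ActiGraph) and −g + 8 ≤ −1 gives g ≥ 9 (activPAL). The permitted maximum is 7. To end before the 48 h period as well, −g + 7 ≤ −3 gives g ≥ 10, and for the activPAL g ≥ 11.

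The SAP's 3-day minimum is met by full pre-randomisation days alone at gaps of 4 to 7 days, but not at 2 or 3. Excluding the restricted period too, only gaps of 6 and 7 days keep 3.

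**Size of the baseline effect, as an outer bound.** Suppose treatment shifts mean daily activity by δ, in full from the day after visit 1. Let f be the share of full ActiGraph days after that visit and β the model's slope on baseline. The baseline then differs between arms by fδ, and the adjusted estimate of a true follow-up difference δ is δ(1 − βf). The documents do not give β, so take 0 to 1.
- Gap of 2 days: f = 5/7 = 0.71, so the estimate lies between δ (β = 0) and 0.29δ (β = 1).
- Gap of 7 days: f = 0, so nothing is lost.
- Gaps equally frequent (assumed): f = 15/42 = 0.36, so the estimate lies between δ and 0.64δ.

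An effect that takes longer than a few days to appear gives a smaller loss.

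**Week 24.** All 7 full ActiGraph days and all 8 activPAL days follow visit 5. Even if the 62 h (2.58 days) started only with the first full day, 7 − 2.58 = 4.42 days lie beyond it, hence at least 4 whole days of 7. Against the protocol's 72 h, 7 − 3 = 4 for the ActiGraph and 8 − 3 = 5 for the activPAL.

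**Holiday rule.** Posting only moves wear later: a delayed baseline may start after randomisation, and a delayed final week moves further from visit 5.

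**The case against.** The best reply is that the problem is narrow, and much of that reply stands.

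- A reader might infer that every baseline holds several days of treatment. The documents do not support that. At a 7-day gap the ActiGraph window ends on the day of visit 1, with no full day after it. Gaps of 4 to 7 days leave at least 3 full days before randomisation. The activPAL always runs past, but SAP 5.2 lists only ActiGraph outcomes.
- A reader might infer that the 24-week week contains no treatment effect. That goes too far. The clinic day and roughly the first 62 h may carry drug effect, and nothing tells participants to drop the diet at visit 5, so a diet effect may persist. No section states the day of the last dose; that dosing ends at visit 5 is inferred from drug return, accountability and the absence of dispensing.
- A reader might infer that the 48 h restriction biases the comparison between arms. Before visit 1 it applies equally to all arms and bars only structured activity, so by itself it does not. It can distort the within-arm changes that Protocol 11.1 describes, because the later windows start after that visit's restriction.
- The week 6 and week 12 windows fall on treatment and are already SAP outcomes, so an on-treatment result is not lost.
- Monitors are applied under site procedures that are not in the documents, and a wear log is kept. Dated truncation may already be feasible or even practised. If so, the SAP should say so.

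What the reply does not remove is that the SAP takes both windows whole, and that for five of the six permitted gaps the ActiGraph baseline includes at least one full day after randomisation.

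**Conclusion.** The point holds. No permitted schedule completes baseline wear before randomisation, and all full days of the 24-week window follow the final visit. As the SAP stands, change in activity to study end may compare a baseline partly affected by treatment with a value mostly off drug, and this tends to dilute an on-treatment effect. The size runs from no full ActiGraph baseline day affected (7-day gap) to 5 of 7 (2-day gap), and at least 4 of 7 days beyond five half-lives at week 24.

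This assumes that dosing ends at visit 5 and that drug and diet start at or just after visit 1. The actual distribution of gaps is not given.

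Severity is low to moderate. It would be tempting to rank this as a defect that must be cured before the trial can be interpreted; the documents do not support that. The endpoint is exploratory, PYY, sample size and safety are unaffected, and the week 6 and 12 follow-up windows are sound. Their models do share the same baseline covariate, so the baseline rule below helps them too.

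**What to change.** **SAP 5.2 and 5.3.3 (useful even if data collection has ended).**
1. Count as baseline only full wear days before visit 1. If fewer than 3 remain (gaps of 2 and 3 days), treat baseline as missing and use the missing indicator method already named in SAP 3.2.1. That section sends the reader to 5.3.2 for detail that is not there, so state the method in the same sentence.
2. Add a sensitivity analysis that also excludes the 48 h restricted period, noting that only gaps of 6 and 7 days then keep 3 days.
3. Label the 24-week window as post-treatment, and present week 12 as the last on-treatment activity result.

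**Protocol, if visits remain.** Move visit 0, with consent, early enough for wear to end before visit 1: at least 8 days for the ActiGraph and 9 for the activPAL, or 10 and 11 to clear the restricted period as well. Posting monitors ahead of the present visit 0 is not a substitute: it would come before consent, and the protocol allows posting only after holidays. Issue the final monitors so that wear ends before visit 5. Make the holiday rule consistent with both.

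**Cost.** A few SAP sentences, some missing baselines (two of the six permitted gaps; four of six in the sensitivity analysis), a wider visit 0 window and some postage.
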